## List of Abbreviations

$\lambda_z$	Terminal elimination rate constant
ADA	Antidrug antibody
ADR	Adverse drug reaction
AE	Adverse event
ALT	Alanine aminotransferase
AST	Aspartate aminotransferase
AUC	Area under the concentration-time curve
AUC 0-∞	Area under the concentration-time curve from zero to infinity
AUC 0-t	Area under the concentration-time curve from zero to time t
CCI	
CI	Confidence interval
C last	Last quantifiable concentration
C max	Maximum concentration
C min	Minimum concentration
CR	Complete response
CRA	Clinical Research Associate
CRF	Case report form
CRO	Contract Research Organization
CSR	Clinical Study Report
CT	Computed tomography
CTCAE	Common Terminology Criteria for Adverse Events
CTLA-4	Cytotoxic T lymphocyte antigen 4
C trough	The concentration observed immediately before next dosing
DCR	Disease control rate
DLT	Dose-limiting toxicity
DNA	Deoxyribonucleic acid
CCI	
ECG	Electrocardiogram
ECOG	Eastern Cooperative Oncology Group
eCRF	Electronic case report form
EOT	End-of-Treatment

ESCC	Esophageal squamous cell carcinoma
FDA	Food and Drug Administration
FFPE	Formalin-fixed, paraffin-embedded
FSH	Follicle-stimulating hormone
GCP	Good Clinical Practice
HAHA	Human antihuman antibody
HIV	Human immunodeficiency virus
IB	Investigator's Brochure
ICF	Informed Consent Form
ICH	International Council for Harmonization
IEC	Independent Ethics Committee
IMP	Investigational medicinal product
irAE	Immune-related adverse event
IRB	Institutional Review Board
IV	Intravenous(ly)
IVRS	Interactive voice response system
LFT	Liver function test
Mb	per megabase
MCC	Merkel cell carcinoma
MMR	Mismatch repair

CCI [REDACTED]

CCI [REDACTED]

MTD	Maximum tolerated dose
NCI	National Cancer Institute
NSCLC	Non-small cell lung cancer

CCI [REDACTED]

PD	Progressive disease/disease progression
----	---

CCI [REDACTED]

CCI [REDACTED]

CCI [REDACTED]

PK	Pharmacokinetic(s)
PR	Partial response
RECIST	Response Evaluation Criteria in Solid Tumors
RP2D	Recommended Phase II dose
SAE	Serious adverse event
SAP	Statistical Analysis Plan
SD	Stable disease
SMC	Safety Monitoring Committee
$t_{1/2}$	Elimination half-life
T4	Thyroxine
TEAE	Treatment-emergent adverse event
TIL	Tumor infiltrating lymphocyte
TLS	Tumor lysis syndrome
$t_{max}$	Time to maximum concentration

CCI [REDACTED]

CCI [REDACTED]

TTR	Time to response
TSH	Thyroid-stimulating hormone
ULN	Upper limit of normal

**1 Synopsis**

Clinical Study Protocol Number	MS100070-0035
Title	A Phase I/Ib Study to Evaluate the Safety, Tolerability, and Pharmacokinetics of Avelumab in Chinese Subjects with Locally Advanced Unresectable or Metastatic Solid Tumors with Expansion to Selected Indication(s)
Study Phase	I/Ib
IND Number	Not applicable
FDA covered study	No
EudraCT Number	Not applicable
Coordinating Investigator	PPD
Sponsor	Merck KGaA, Darmstadt, Germany
Sponsor Legal Representative in the European Union	Merck KGaA, Darmstadt, Germany
Study centers/countries	The study will be conducted at approximately 3 sites in mainland China.
Planned study period (first subject in-last subject out)	First subject in: Q1 2018 Last subject out: Q4 2019
Trial Registry	Clinicaltrials.gov Chinadrugtrials.org.cn

Objectives:
 
Primary Objectives:
 
 
• To evaluate the maximum tolerated dose (MTD) of avelumab (MSB0010718C) monotherapy in Chinese subjects.
 
• To characterize the pharmacokinetics (PK) of avelumab in Chinese subjects.
 
 
Secondary Objectives:
 
 
• To determine the safety and tolerability of avelumab by assessing treatment-emergent adverse events (TEAEs) and treatment-related adverse events (AEs) for all dose groups according to the National Cancer Institute (NCI)-Common Terminology Criteria for Adverse Events (CTCAE) Version (v) 4.03 in Chinese subjects.
 
• To characterize immunogenicity of avelumab in Chinese subjects.
 
	

CCI

**Methodology:**

This is a Phase I/Ib, open-label, dose-escalation study.

Dose escalation will be performed at the following 3 dose levels, subjects will receive avelumab by intravenous (IV) infusion over 1 hour once every 2 weeks:

- 3 mg/kg
- 10 mg/kg
- 20 mg/kg

The dose escalation uses a modified “3 + 3” design. Thus, 3 or 6 subjects will be enrolled at each dose level. The decision to escalate to the next dose level will be based on safety assessments after all subjects of a cohort have reached Day 21 (dose-limiting toxicity [DLT] observation period). In order to assess the safety of avelumab, a Safety Monitoring Committee (SMC), responsible for dose escalation decisions, will be established. Safety and tolerability of avelumab at a given dose level in Chinese subjects will be confirmed if no DLT observed in the first 3 subjects or less than 2 out of 6 subjects in the corresponding dose cohort.

Once the safety of avelumab at 20 mg/kg once every 2 weeks have been established and can be regarded as safe (ie, no DLT observed in the first 3 subjects or less than 2 out of 6 subjects experience a DLT), a new cohort of 10 mg/kg administered once weekly can be immediately initiated in 6 evaluable subjects to assess safety of a more frequent dosing. Subjects in this cohort of 6 evaluable subjects will receive avelumab once weekly at a dose of 10 mg/kg for 12 consecutive weeks (10 mg/kg once weekly cohort) and then starting at Week 13, once every 2 weeks thereafter (this cohort will not be subjected to DLT evaluation as a primary endpoint).

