ADA: antidrug antibody; AE: adverse event; CR: complete response; CT: computed tomography; D: Day; DLT: dose-limiting toxicity; ECG: electrocardiogram; ECOG PS: Eastern Cooperative Oncology Group performance status; EOT: End-of-Treatment; hCG: human chorionic gonadotropin; HIV: Human immunodeficiency virus; ICF: Informed consent form; IMP: investigational medicinal product; MRI: magnetic resonance imaging; PD: progressive disease; CCI: [redacted] PK: pharmacokinetics; PR: partial response; RECIST: response evaluation criteria in solid tumors; SAE: serious adverse event; T4: thyroxine; TSH: thyroid-stimulating hormone; V: Visit; W: Week.

1. A time window of up to 3 days before or 1 day after the scheduled visit day (- 3/+ 1 days) is permitted for all study procedures (except for PK sampling visits on Day 2 and 3, see [Table 1-3](#)). The calculation of the dose of avelumab will be based on the weight of the subject determined within 72 hours prior to the day of drug administration.
2. All subjects will have an EOT Visit within 7 days after the decision to discontinue avelumab. In addition, subjects will be followed every 12 weeks ( $\pm 7$  days) for survival (including assessment of any further anticancer therapy).

CCI

[figure not shown]
4. If another anticancer therapy is administered before the end of this 7-day period, the EOT Visit should be conducted prior to the start of this new therapy, if possible. The EOT Visit may be performed on the day of the decision to discontinue avelumab.

CCI

7. Medical history should include history of cancer, previous and ongoing medications, previous surgeries, radiotherapies, baseline medical conditions, smoking and alcohol history, and family cancer history.
8. A full physical examination will be conducted at Clinical Screening, at the EOT Visit and at the 30-day Safety Follow-up Visit. During the Treatment Phase, the physical examination will be symptom-directed.
9. If the Clinical Screening ECOG PS was performed within 3 days prior to Day 1, it does not have to be repeated at Visit 1/Cycle 1 Day 1.
10. Enrolment will be done after confirmation that the subject meets all screening inclusion criteria ([Section 5.3.1](#)) without matching any exclusion criterion ([Section 5.3.2](#)).

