11. The observation period for DLTs is the 21-day period after the first administration of avelumab for subjects with data used for implementing the dose-escalation algorithm for dose determination (the DLT assessment is not applicable for the 6 subjects in 10 mg/kg once weekly cohort).
12. Core serum chemistry includes liver function panel (alkaline phosphatase, aspartate aminotransferase, alanine aminotransferase, bilirubin), acute chemistry panel (sodium, potassium, chloride, blood urea nitrogen/total urea, creatinine, glucose), and mineral panel (magnesium, phosphorus, calcium). If full and core chemistry are scheduled at the same visit, the full chemistry will be performed.
13. Full chemistry panel and other laboratory studies are detailed in [Section 7.4.3](#). Follicle-stimulating hormone at Clinical Screening, if applicable.
14. Full urinalysis (protein content required, and optional parameters albumin and immunoglobulin G to be tested depending on study site capability) at Clinical Screening/baseline, and EOT; basic urinalysis (protein content only) on Days 43 and 85, and then every 6 weeks thereafter prior to administration of avelumab. If urinalysis (full or basic) is positive for protein, sediment will be evaluated.
15. In serum at Clinical Screening; in urine thereafter. Results of the most recent pregnancy test should be available prior to next administration of avelumab.

CCI

CCI

21. Premedication is mandatory approximately 30 to 60 minutes prior to the first 4 doses of avelumab. Premedication should be administered for subsequent avelumab doses based upon clinical judgment and presence/severity of prior infusion reactions. This regimen may be modified based on local treatment standards and guidelines as appropriate. However, the prophylactic use of systemic corticosteroids is not permitted.
22. Concomitant medications and procedures will be documented at each study visit until the 30-day Safety Follow-up Visit.
23. All AEs will be documented at each study visit until the 30-day Safety Follow-up Visit. After this visit, only treatment-related nonserious AEs have to be documented until the 90-day Safety Follow-up Phone Call.

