## 2.1 Safety Monitoring Committee

To ensure subjects' safety during the study, a Safety Monitoring Committee (SMC) will review the safety data on a regular basis. The SMC consists of permanent members from the Sponsor (eg, but not limited to, early development lead, medical lead, and Global Patient Safety representative), the Coordinating Investigator as well as of ad hoc members (eg, but not limited to, all participating Principal Investigators [as applicable]). During the study, the SMC will evaluate the safety data and will decide on dose-limiting toxicities (DLTs) relevant for the treatment and will advise on dose escalation or suspension of enrolment, with the final adjudication being a Sponsor prerogative. In 10 mg/kg once weekly cohort, the SMC will evaluate overall safety data when all 6 subjects have completed minimum 4-week treatment period, and after 12 weeks of observation has been completed for all subjects enrolled in this cohort. The SMC may modify the frequency of meetings as deemed appropriate by the SMC during the course of the study.

The membership and specific working procedures of the SMC will be described in an SMC Charter, which will be established prior to the start of subject recruitment.

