In 10 mg/kg once weekly cohort, the SMC will evaluate overall safety data when all 6 evaluable subjects have completed a minimum 4-week treatment period, and after 12 weeks of observation has been completed for all subjects enrolled in this cohort (see Section 2.1).

See Section 5.1.2.1.2 and Figure 5-3 for further details of the dose escalation algorithm, and Section 5.2.2 for a discussion of the rationale for dose selection.

Subjects will not be replaced unless the subject does not fulfill the requirement for dose determination. Dose determination is achieved when the subject receives 2 doses of avelumab at the scheduled regimen and completes the minimal 21-day safety observation period (DLT observation period) unless they discontinue due to a DLT. For the definition of a DLT, see Section 7.4.1.1.

The design of the dose escalation is based on Studies EMR100070-001 and EMR100070-002 and therefore allows for the ethnic sensitivity of avelumab to be evaluated across studies.

The overall study design is shown in Figure 5-1.

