**Figure 5-3 Dose Escalation Algorithm for Doses up to 20 mg/kg of Avelumab**

DLT: dose-limiting toxicity; Q2W: every 2 weeks; QW: every week.

At the conclusion of the 21-day DLT observation period for each cohort (excluding 10 mg/kg once weekly cohort), a data review will be conducted. The SMC (including Principal Investigators), is responsible for making dose escalation decisions. The SMC will decide whether or not to escalate the dose of avelumab to the next level, or whether an interim dose level will be added by reviewing the safety data after all subjects of a cohort have completed the DLT observation period (see Section 2.1 and SMC Charter).

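### Escalation can be decided at Day 21, but in the once-every-2-weeks cohorts no visit, AE query or safety laboratory test is scheduled between the day of dose 2 (Day 15) and Day 29

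*Protocol*

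**What the plan says.** Two protocol passages set the timing of the escalation decision. The Synopsis (Methodology) makes it "based on safety assessments after all subjects of a cohort have reached Day 21". The text under Figure 5-3 in Section 5.1.2.1.2 says "At the conclusion of the 21-day DLT observation period for each cohort (excluding 10 mg/kg once weekly cohort), a data review will be conducted", and has the SMC decide "after all subjects of a cohort have completed the DLT observation period (see Section 2.1 and SMC Charter". Neither passage asks for later data.

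Section 5.1.1.1 makes dose 2 part of what is judged: "Dose determination is achieved when the subject receives 2 doses of avelumab at the scheduled regimen" and the subject completes at least 21 days of observation, unless a DLT ends treatment first. Table 1-1 footnote 11 agrees on the period: "The observation period for DLTs is the 21-day period after the first administration of avelumab".

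For these cohorts Table 1-1 has visits on Days 1, 15 and 29, and marks DLT assessment at Days 1 and 15 only. Hematology and core chemistry are due on Days 15 and 29. Section 7.4.3 puts blood sampling before the infusion. Section 7.4.1.2 ties the AE query to study visits. Footnote 1 allows "A time window of up to 3 days before or 1 day after the scheduled visit day".

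The SAP (Sections 8.2 and 15.1) defines the DLT period and the DLT Analysis Set. It says nothing on the SMC or on when escalation is reviewed.

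**The concern.** The DLT window runs to Day 21 and is meant to include the response to a second dose. The last scheduled safety laboratory sample inside it is taken before that dose, and the last scheduled AE query is at the dose 2 visit. The next of either comes after the point at which the SMC may decide.

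A review run exactly as written could therefore count a cohort as free of DLTs with no scheduled laboratory result that reflects dose 2. What is at stake is mainly the escalation decision, which serves the primary MTD objective. The DLT table in the study report is much less exposed. By contrast, the weekly cohort, which has no DLT evaluation, has laboratory tests scheduled on Days 8, 15 and 22 (Table 1-2), and its SMC review follows at least 4 weeks of treatment (Section 2.1).

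**Working it through.** **Plan's own figure.** The planned 21 subjects (up to 24) reproduce as 3 + 6 + 6 + 6 = 21, or 24 if the 3 mg/kg cohort expands to 6. This is not in dispute and supplies only the cohort sizes used below.

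**Length of the gap.** Inputs: visit days and window from Table 1-1 and footnote 1; DLT period from footnote 11.

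1. Dose 2 is on Day 15, or Days 12 to 16 with the window (15 − 3, 15 + 1).
2. Days left to Day 21 are 21 − 15 = 6, ranging from 21 − 16 = 5 to 21 − 12 = 9. As shares of the window: 6/21 = 29%, 5/21 = 24%, 9/21 = 43%.
3. Visit 3 is on Day 29, or Days 26 to 30. No permitted window brings it to Day 21 or earlier.
4. Table 1-3 adds PK samples on Days 2, 3 and 8, but nothing between Days 15 and 29. Some assessment rows of Table 1-1 are blacked out, but no visit column is.

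**What is scheduled after dose 2 on Day 15 itself.** Two hours of observation (Sections 6.4 and 6.5.4), a post-infusion ECG at the first three doses (Section 7.4.4) and an end-of-infusion PK sample (Table 1-3).

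**What other reporting covers in the gap.** SAEs within 24 hours of awareness (Section 7.4.1.4), nonlaboratory Grade 4 and 5 events as SAEs (Section 7.4.1.1), and weekly repeats of significant abnormalities already found (Section 7.4.3). Two classes remain: nonserious Grade 3 events that the subject does not volunteer, and new laboratory abnormalities that would qualify as AEs under Section 7.4.1.1.

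**Exposure if the next level opens at Day 21.** Day 29 data arrive 29 − 21 = 8 days later (5 to 9 with windows). A new once-every-2-weeks subject has dose 2 due on Day 15 (earliest Day 12), so receives one dose in that time. A weekly subject has dose 2 due on Day 8 (7 to 9), so receives up to two.

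**Illustration only.** The documents give no DLT rate, onset pattern or missed fraction, so all three are assumed. Let p be the true DLT rate, with onset uniform over 21 days, and m the fraction of events in the 6-day gap that are unknown at review. The rate seen at review is q = p(1 − m × 6/21).

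- Six slots opened together (10 mg/kg), pass if fewer than 2 of 6: (1 − q)^6 + 6q(1 − q)^5.
- Staggered 3 + 3, with the first three fully known by the second review: (1 − q)^3 + 3q(1 − p)^2(1 − q)^3.

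Example: p = 1/3 and m = 0.5 give q = 0.2857, a six-slot pass probability of 0.452 and a staggered one of 0.503.

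| Assumed p | Six-slot: m = 0 / 0.5 / 1 | Staggered: m = 0 / 0.5 / 1 |
|---|---|---|
| 5% | 96.7 / 97.5 / 98.3% | 97.3 / 97.9 / 98.3% |
| 10% | 88.6 / 91.3 / 93.7% | 90.6 / 92.3 / 94.0% |
| 1/6 | 73.7 / 79.3 / 84.6% | 78.0 / 81.7 / 85.3% |
| 1/3 | 35.1 / 45.2 / 56.2% | 42.8 / 50.3 / 58.3% |

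The six-slot column puts all six subjects in the gap at once. If only the last 1, 2 or 3 enrolled are in it, with p = 1/3 and m = 0.5, the result is 36.7%, 38.3% or 40.0%. The m = 1 values are upper bounds for a 6-day gap, because they also count as missed the events that SAE reporting would catch.

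**The case against.** The strongest reply is that the protocol asks for more than visit-based reporting. Section 5.1.2.1.2 says DLTs are assessed during the 21 days. Section 7.4.1.6 has AEs recorded continuously. Subjects are told to report delayed reactions at once (Sections 6.4 and 6.5.5.1), investigators must watch closely for immune-related events (Section 6.5.4), and symptom-directed examination is available throughout treatment. All of this stands and narrows the gap. None of it schedules a contact or a test after the day of dose 2.

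Second, the wording sets an earliest time and does not forbid waiting. The "specific working procedures of the SMC will be described in an SMC Charter", to be in place before recruitment, and the timing sentence itself refers to that Charter. This stands: the Charter may already require Day 29 data, and these documents cannot show whether it does.

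Third, the SMC confirms every DLT, so an adjudicator exists for an abnormality first seen on Day 29. That is true, but neither document says how it should treat uncertain onset. The SAP rule in Section 15.2 covers incomplete dates only, and here the recorded date would be complete.

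Four stronger readings are tempting, and the documents do not support them:

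- That no scheduled data at all follow dose 2. The Day 15 observation, ECG and PK sample do.
- That the SAP also permits the Day 21 review. It is silent on this.
- That the reported DLT endpoint is compromised. AEs carry onset dates (Section 7.4.1.2), DLTs are taken from the AE form (SAP Section 15.1), and the cutoff is Week 13 of the last subject (SAP Section 6.2), after every Day 29 visit. Only a laboratory abnormality first seen on Day 29 escapes this protection.
- That the pass probabilities measure the risk of a wrong final conclusion. A missed event can surface on Day 29, and the SMC "will advise on dose escalation or suspension of enrolment".

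**Conclusion.** The point holds as a mismatch within the protocol between review timing and visit schedule. About 6 of 21 DLT days (29%; 5 to 9 days, 24% to 43%, with windows) have no scheduled visit, AE query or safety laboratory test by the time the SMC may decide.

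The effect on decisions cannot be estimated from the documents. At assumed DLT rates of 5% to 10%, closer to the tolerability the protocol reports (Sections 3.2.1 and 5.1.1.1), missing every event in the nominal 6-day gap moves the pass probability by only about 1 to 5 percentage points. The shift becomes large only at high assumed rates. The consequence is also bounded: one dose per newly started subject at the next level, or up to two in the weekly cohort, before Day 29 data arrive.

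It still merits correction. It touches the decision rule for a primary objective, and data already scheduled can close the gap. The conclusion rests on the Charter not already doing so.

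**What to change.** Reconcile the timing sentences in the Synopsis and under Figure 5-3 with Table 1-1 and its footnote 11, or cite the Charter section that does so. The SMC data set should cover the whole 21-day window, including the days after dose 2. One example is to use the Day 29 pre-dose AE query and laboratory results, or End-of-Treatment results for subjects who stopped earlier. Reconcile this with the text in the Synopsis and Section 5.1.1.1 that lets the weekly cohort start at once after 20 mg/kg is regarded as safe.

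State how the SMC counts an abnormality first seen on Day 29 with uncertain onset, and report the DLT tally with and without such events. If reviews have already been held, record what data were available at each.

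If Day 29 data are used, the real cost is time: about 8 days per escalation step (5 to 9 with windows). That is 3 × 8 = 24 days over three steps (15 to 27), or 5 × 8 = 40 days (25 to 45) if both staggered cohorts expand and all five reviews wait. No visit or blood draw is added, since Section 7.4.3 already requires results essential for subject management to be reviewed before dosing. No dose, DLT definition, window length or escalation threshold changes.

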**Planned number of subjects:**

Approximately 21 subjects (up to approximately 24 subjects).

**Primary endpoints:**

- Occurrence of DLTs during the DLT observation period (first 21 days of treatment; excluding 10 mg/kg once weekly cohort).
- PK profiles in Chinese subjects.

**Secondary endpoints:**

- Occurrence of TEAEs for all dose groups according to NCI-CTCAE v4.03.
- Occurrence of treatment-related AEs for all dose groups according to NCI-CTCAE v4.03.
- Serum titers of antidrug antibodies (ADA) against avelumab.

CCI

**Pharmacokinetics:**

- $AUC_{0-t}$ : area under the concentration-time curve from time zero to time t (calculated by linear trapezoidal summation).
- $AUC_{0-\tau}$ : area under the concentration-time curve from time zero to tau, the respective dosing interval, ie, one- or two-week (calculated by linear trapezoidal summation).
- $AUC_{0-\infty}$ : area under the concentration-time curve from time zero to infinity (calculated by linear trapezoidal summation and extrapolated to infinity using the last quantifiable concentration/terminal elimination rate constant [ $C_{last}/\lambda_z$ ]).
- $\lambda_z$ : terminal elimination rate constant. The value of  $\lambda_z$  is determined from the slope of the regression line of log (concentration) versus time.
- $C_{max}$ : maximum serum concentration.
- $C_{trough}$ : serum concentration observed immediately before next dosing.
- $C_{last}$ : last quantifiable concentration.
- $t_{max}$ : time to maximum concentration.
- $t_{1/2}$ : elimination half-life determined as  $0.693/\lambda_z$ .

